#### Swallowing Frequency:

Swallowing frequency is analyzed by sEMG signals recorded on the KayPentax Digital Swallow Workstation™ with integrated digital swallowing signals lab (DSW™, Model 7120, New Jersey). A three-sensor sEMG electrode (Uni-Patch™, Disk #7500, Covidien Corporation, Tyco Healthcare, Wabasha, MN) will be placed on the anterior neck skin under the chin, over the submental muscles above the hyoid bone. Each patch will include two recording electrodes and a third ground electrode. Spontaneous swallowing frequency is calculated as the number of swallows per minute (SPM) for 10 minutes on room air and then for each HFNC intervention. Swallows will be counted from the visual myographic waveform produced by the DSW.

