### Spontaneous Swallowing Frequency:

Spontaneous swallowing is an airway protection reflex and the measurement of its frequency is considered to be a sensitive indicator of swallow function. This index can sensitively identify dysphagia and other swallowing-related disorders. Furthermore, the reduction in this index is associated with increased level of secretions and chest infections. One modality used to measure swallowing frequency is surface electromyography (sEMG), which records electric activity during swallow via an electrode placed on the skin under the chin. This non-invasive technology has been used for more than 20 years to record various aspects of swallowing physiology. In this study, sEMG will be used because of its feasibility, accuracy, and ability to detect a swallow.

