### Swallowing Effort and Timing:

Swallowing effort via submental sEMG provides an objective measurement of lingual and sub-mental muscle activity during the act of swallowing. Measurements include muscle contraction amplitude and contraction timing/speed. Clinically, swallowing effort parameters have been used to document normative values in healthy individuals, as well as to document the effects of a disease on swallowing. Prior research has shown that both amplitude and timing are influenced by multiple factors including the volume and viscosity of the item (or bolus) being swallowed, and the age and gender of the person swallowing. However no study has investigated the effects of HFNC on either swallowing effort parameter.

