The AIRVO 2 high-flow nasal cannula system (Fisher and Paykel Healthcare Limited, Panmure, Auckland, New Zealand) will be used. Nasal prongs sizes are chosen as per manufacturer recommendations. Participants will receive three levels of HFNC flow rates (30, 45, and 60 L/min) through nasal prongs. If a small-size nasal prong is used, the participant will receive 30, 45, and 50 L/min flow rates instead of 30, 45, and 60 L/min, as manufacturer recommendations state the maximum liter flow for a small-size nasal prong is 50 L/min. Oxygen concentration will be set at 21% and a temperature of 37 °C. First, individuals will be placed on the sEMG monitor. Following the application of the sEMG, each participant will sit quietly for 10 minutes, before being attached to the HFNC, so a baseline swallow frequency can be established. After the baseline swallow frequency is established, each participant will be asked to swallow 8 boluses: 2 trials of water at 2 volumes (5 and 10 mL) and 2 trials of applesauce at 2 volumes (5 and 10 mL). Participants will rest for 15 seconds after completing each swallow. This procedure will establish the participant's baseline swallowing effort measurements. Once these swallows have been completed, the participant will be placed on the HFNC. Each participant will be placed on three different flow rates (30, 45, and 60 L/min or 30, 45, and 50 L/min) in random order. The random order will be generated by an online random number tool (<https://www.randomizer.org>). The study participant will be subjected to each flow rate for 15 minutes. During the first 10 minutes, swallow frequency will be recorded. After 10 minutes at the given flow, the participant will complete the 8 aforementioned swallows. After completing all of the swallowing trials, the participant will be removed from the HFNC for a period of 10 minutes. This process will be repeated for all three

flowrates for a total of 32 boluses swallowed.

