### **Risk to subject:**

- Risks include aspiration of water or applesauce when swallowing on the HFNC. Discomfort and dryness of mouth or nose due to the use of the high flow. Also, since the swallowing measurement device is applied through patch to skin, allergic reaction may occur. Participants will be closely monitored by the study investigators and if any signs of aspiration (coughing, shortness of breath), discomfort, or allergic reaction occurs, the session will be terminated and the participant will be withdrawn from the study.

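### Spontaneous swallows are identified only by eye from one submental trace, with no concurrent check and quiet sitting stated only for baseline, so miscounting that differs by condition could bias swallow frequency

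*Combined protocol and SAP*

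**What the plan says.** The Swallowing Frequency section defines the outcome: "Spontaneous swallowing frequency is calculated as the number of swallows per minute (SPM) for 10 minutes on room air and then for each HFNC intervention". The signal comes from one three-sensor patch that "will be placed on the anterior neck skin under the chin, over the submental muscles above the hyoid bone". Identification is visual: "Swallows will be counted from the visual myographic waveform produced by the DSW".

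The background section on spontaneous swallowing justifies the method by stating that "sEMG will be used because of its feasibility, accuracy, and ability to detect a swallow". The background section on effort and timing says that submental sEMG "provides an objective measurement of lingual and sub-mental muscle activity during the act of swallowing".

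On behaviour during recording, the HFNC paragraph under Experimental Design and methods says that "each participant will sit quietly for 10 minutes, before being attached to the HFNC". The procedure outline that begins with application of the sEMG monitor repeats this for baseline. Neither place gives a behavioural instruction for the three 10-minute recordings on HFNC.

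The Risk to subject section lists "Discomfort and dryness of mouth or nose due to the use of the high flow" among the risks. It also says "Participants will be closely monitored by the study investigators", and that the session ends if coughing or shortness of breath (as signs of aspiration), discomfort or an allergic reaction occurs.

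No section gives an amplitude, duration or shape criterion for a swallow, a second signal, an event log, an exclusion rule for other muscle activity, a second reader, or masking of the reader to flow.

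**The concern.** Bolus swallows are cued, so the reader knows that they happened and roughly when. Spontaneous swallows are not cued, and the trace is the only evidence for them. By the protocol's own description the sensor responds to tongue and submental muscle. The protocol says this about the act of swallowing; that the same muscles also reach the sensor when they move for other reasons is an inference, but a short one.

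There are two ways for error to differ by condition. Non-swallow movement may differ between a baseline with an instruction to sit quietly and HFNC periods with none stated, or between flows. Recognition of a true swallow may also shift: the study asks whether HFNC changes the amplitude and timing of the swallow waveform, and those are features that a reader is likely to use.

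The frequency comparison is at stake. The background section treats a fall in this index as the warning sign. Extra counts on HFNC could mask a fall, and missed swallows could create one. Random flow order and within-person comparison remove stable differences between people, but not an error tied to the condition itself.

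**Working it through.** The plan gives no swallow rate, SD, error rate, reader agreement or power calculation, so there is no figure of its own to reproduce.

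**Step 1. What cancels and what does not.** For one participant with true count λ per 10 minutes in every condition, let s be the share of true swallows recognised and f the number of non-swallow bursts counted. The expected count in condition c is λ·s_c + f_c. The difference from baseline is

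λ(s_c − s_0) + (f_c − f_0).

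It is zero only if recognition and false counts are the same in both conditions, or happen to offset each other.

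**Step 2. Size of one event.** Assume λ = 6 (not in the documents).
- One extra count in one condition: 7/6 − 1 = +16.7%.
- Two extra counts: 8/6 − 1 = +33.3%.
- One missed swallow: 5/6 − 1 = −16.7%.
- True fall from 6 to 5 with one extra count: 5 + 1 = 6, so the fall reads as 0%.

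These lines restate the assumption as a percentage. They show sensitivity to one event; they do not estimate the bias.

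**Step 3. Effect on the planned test.** From the documents: n = 50, 10-minute recordings, baseline plus three flows, one-way repeated measures ANOVA, p < .05. Assumptions: baseline enters as a fourth level; Poisson counts; between-person CV 0.5; true rate 0.5 or 1.0 per minute, equal in all conditions; false counts as shown. There were 4,000 runs per setting, so the simulation standard error is at most √(0.25/4000) ≈ 0.8 percentage points.

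| False counts per 10 min (baseline and three flows) | Chance of p < .05, 0.5/min | Chance of p < .05, 1.0/min |
|---|---|---|
| None | 5.3% | 5.2% |
| Rising linearly from 0 to 0.5 | 13.4% | 9.6% |
| Rising linearly from 0 to 1 | 43.0% | 24.7% |
| Rising linearly from 0 to 2 | 95.4% | 75.0% |
| 0 at baseline, 1 at every flow | 55.8% | 31.2% |
| 2 in all four conditions | 5.1% | 4.6% |

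There is no true flow effect in any row, so anything above about 5% is spurious. The last row matters most: false counts that are equal across conditions do not produce a false flow effect. In this illustration the harm comes from the difference between conditions, and an average of 1 to 2 counts per 10 minutes is enough.

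**Step 4. Do the documents make such a difference plausible?** Quiet sitting is stated for one of the four recordings. Mouth and nose discomfort and dryness are listed as effects of the device. A change in the swallow waveform is itself under study. That supports a risk. It gives no rate, no gradient across flows and no sign.

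**The case against.** Several stronger readings are tempting, and the documents do not support them.

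- **That any muscle burst counts as a swallow.** The plan says that swallows are counted from the waveform, so the reader judges which deflections are swallows. The criterion is unstated, which is a narrower defect.
- **That false counts rise with flow.** The Risk to subject section ties dryness and discomfort to use of the device, with no gradient across flows. The Introduction says that humidified gas improves comfort, which points the other way.
- **That coughing or speech drives the error.** Coughing as a sign of aspiration ends the session, as does discomfort, so those sources are at least partly removed. The Introduction's remark that HFNC permits talking gives no reason for speech to increase with flow, since people can also talk on room air.
- **That the bias flatters HFNC.** Missed swallows would act in the opposite direction.

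It is also fair to say that the Specific Aims place the frequency measurement at rest, so quiet sitting may be intended throughout. The protocol also cites work on identifying swallows from sEMG in healthy adults, which may contain usable criteria. Neither point closes the gap: the instruction is not written for the HFNC periods, and the protocol adopts no criterion from that work.

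A last objection concerns the remedy and stands in full. The bedside observer knows the flow. Requiring the observer's mark before a burst counts, or rejecting every burst that coincides with tongue movement (which the protocol itself describes as part of swallowing), could create a flow-related bias of its own.

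**Conclusion.** The point holds as a risk of differential miscounting in part of the primary aim. It rests on three features of the text: visual identification from a single submental trace, no concurrent check, and quiet sitting stated only for baseline. The bias is not demonstrated, and the documents settle neither its direction nor its size. The ±17% assumes 6 true swallows per 10 minutes and one error in one condition. The simulated rates assume Poisson counts, a CV of 0.5 and chosen false-count patterns. A reader might infer that frequency will be inflated at high flow; the plan does not establish that. What can be said is that small differences in error between conditions could produce or hide a flow effect, and that the plan has no means of detecting them. The change is worth making before recording starts, because events that were not logged cannot be recovered from a single-channel trace.

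**What to change.** Amend the HFNC paragraph under Experimental Design and methods, the Swallowing Frequency section and the procedure outline as follows.

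1. Give the same quiet-sitting, no-talking instruction (except to report a problem) in all four 10-minute recordings.
2. Have the investigator already present time-stamp visible laryngeal elevations and clear non-swallow events (speech, throat clearing, jaw opening without a swallow) in the same way in every period.
3. Fix a waveform criterion for a swallow in advance. Have coded traces, with the log but without the flow, counted by a reader who does not know the condition. For the primary count, exclude only bursts that match a logged non-swallow event with no laryngeal elevation.
4. Report two sensitivity analyses: the waveform-only count, and the count restricted to bursts with a logged laryngeal elevation.

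Do not make a logged elevation a requirement for the primary count. The exclusion in item 3 still draws on an observer who knows the flow, and the waveform-only count shows how much the result depends on it. If the counts disagree, that shows sensitivity to identification; it does not show which count is right.

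Cost: a log or event key and slightly more reading time. Some swallows are hard to see and will go unmarked, which lowers only the elevation-confirmed sensitivity count.

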## Specific Aims

The primary aim of this research is to determine the impact of different flow rates of a high-flow nasal cannula on spontaneous swallowing frequency at rest and swallowing effort and timing while swallowing.

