#### Swallowing Effort:

Both swallowing amplitude and timing parameters will be obtained by analyzing the individual graphic waveforms produced by the DSW algorithm. Measures will be obtained for each of the 8 swallows, at each of the HFNC flow rates.

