### **Special Precautions:**

- All study material will be coded to de-identify participants and a separate list will be kept with the participant's ID and name.

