**Confidentiality:**

- The study investigators, along with the IRB, will have access to the individual participant's results. Neither names nor personal information will be recorded or included in the data analysis. The investigators will strictly adhere to IRB guidelines to ensure that participant's confidentiality is maintained.

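### Swallowing frequency is counted from the visual sEMG waveform, and the plan does not require whoever counts to be unaware of the flow rate

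*Combined protocol and SAP*

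**What the plan says.** The Specific Aims section places the "impact of different flow rates of a high-flow nasal cannula on spontaneous swallowing frequency at rest" within the primary aim. The Swallowing Frequency section defines the outcome: "Spontaneous swallowing frequency is calculated as the number of swallows per minute (SPM) for 10 minutes on room air and then for each HFNC intervention". It then gives the method of measurement: "Swallows will be counted from the visual myographic waveform produced by the DSW". It describes no automated detection, and it does not say who counts, what waveform qualifies as a swallow, or whether the counter knows the flow. Blinding and masking are not mentioned anywhere in the document.

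The nearest text concerns identity. Special Precautions states: "All study material will be coded to de-identify participants and a separate list will be kept with the participant's ID and name". Experimental Design and methods likewise assigns each participant a code number for privacy. Neither covers flow, period or age group.

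Two further statements bear on who knows what. Under Risk to subject, "Participants will be closely monitored by the study investigators". Under Confidentiality, "The study investigators, along with the IRB, will have access to the individual participant's results". Nothing separates these people from those who read the traces.

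For the bolus swallows, Swallowing Effort says: "Both swallowing amplitude and timing parameters will be obtained by analyzing the individual graphic waveforms produced by the DSW algorithm". Plans for Data Analysis defines swallowing speed from the onset and offset of contraction, without saying whether software or a person marks those points.

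**The concern.** The frequency outcome depends on deciding which bursts on a 10-minute submental trace are swallows. The protocol itself describes the signal as lingual and submental muscle activity, and it specifies one electrode patch with no second signal to confirm a swallow. Some bursts may therefore be open to judgement.

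Random miscounting adds noise, which a larger sample reduces. Miscounting that varies with the known flow is different: it shifts the condition means, and no number of participants removes it. It could create an apparent flow effect or cancel a real one.

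Randomising the order of the three flows does not protect against this, because it balances order and does not hide flow from a reader. The baseline is always recorded first and off HFNC, so anyone reading a participant's recordings in sequence can recognise it.

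**Working it through.** The plan states no figure on this point, so there is none to reproduce. The check has two parts.

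**1. Is masking supplied anywhere?** Set side by side, the Swallowing Frequency section makes the outcome a visual count, the identity coding leaves condition uncovered, and the randomisation text (under HFNC, in Experimental Design and methods) says nothing about concealing flow from readers. The introductory section on spontaneous swallowing cites the accuracy of sEMG, but that is a general statement about the technology and gives no reader agreement or counting rule. The plan therefore permits unmasked reading. It also permits masked reading.

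**2. How large could the effect be?** From the documents: n = 50, alpha = 0.05, a 10-minute window (so one swallow = 0.1 swallows per minute, SPM), and a one-way repeated measures ANOVA for frequency. Everything else is assumed: a mean count L of 5 to 10 per window, a within-person variance of phi × L with phi from 1 to 1.5, no true effect, and a flow-dependent miscount of 5% or 10% of L. The miscount b is then 0.05 × 5 = 0.25 up to 0.10 × 10 = 1.0 swallow per window.

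*Single paired contrast.* SE = sqrt(2 × L × phi / 50), z = b/SE, and false-positive rate = P(|N(z,1)| > 1.96).
- Smallest case (L = 5, phi = 1.5, 5%): SE = sqrt(15/50) = 0.548, z = 0.25/0.548 = 0.46, rate 7.4%.
- Largest case (L = 10, phi = 1, 10%): SE = sqrt(20/50) = 0.632, z = 1.0/0.632 = 1.58, rate 35%.
- Ranges: 7.4% to 12.4% for a 5% miscount, and 15% to 35% for 10%.

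*Planned omnibus ANOVA, same assumptions, sphericity assumed.* The noncentrality is 50 × (sum of squared deviations of the condition means) / (phi × L). The sum of squares is b²/2 for a linear drift over three flows, 5b²/9 for a linear drift over baseline plus three flows, and 3b²/4 for a step between baseline and all HFNC conditions.

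| Pattern of miscount | 5% miscount | 10% miscount |
|---|---|---|
| Linear, three flows | 6.6–9.8% | 12–27% |
| Linear, four conditions | 6.4–9.3% | 11–25% |
| Step, baseline vs HFNC | 6.9–10.9% | 13–33% |

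With more dispersion (phi = 3), the 10% linear drift over three flows gives only 8% to 12%.

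*Planned ANOVA, different assumptions.* Take a residual SD of 0.2, 0.3 or 0.4 SPM, four conditions and a linear drift. A drift reaching one swallow per window at the top flow gives 57%, 28% and 17%. A drift of two swallows gives over 99%, 84% and 57%.

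*Hiding an effect.* If the true linear change is 0.2 SPM at the top flow and the SD is 0.3, an opposite drift of 0.1 SPM cuts power from 84% to 28%.

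Across these scenarios the rate runs from about 6% to over 99%. The spread comes from the assumptions. The documents give no swallow rate, variance or reader error with which to narrow it.

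**The case against.** The strongest reply is that this is silence and not a stated flaw. The plan does not say who reads the traces, when, or with what labels, so a masked reading would comply with it. A reader might infer that the trial is declared open-label and that traces will be read with the flow in view. The documents do not support that: the term does not appear, and monitoring of participants by investigators does not make those investigators the readers. This part of the objection stands. What remains is that masking is not required.

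A second objection is that no direction of bias is evident. The aim is non-directional and the Introduction calls prior results contradictory, so nothing points to a consistent lean across 50 people. This lowers the likelihood of bias but does not exclude it, since an individual reader may still hold an expectation.

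Third, a reader might take a figure such as 15% to 35% as the trial's false-positive rate. It is not. It comes from an assumed 10% miscount and a paired contrast that is not the planned test.

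Fourth, it is tempting to say that the bolus measurements carry the same risk. The Swallowing Effort section refers to waveforms from the workstation's algorithm and does not show manual marking. Those swallows are also prompted, with eight per condition, so deciding whether a swallow occurred does not arise in the same way. That concern is conditional only.

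**Conclusion.** The point holds as a gap in how a primary-aim outcome is protected. The frequency count depends on visual reading, the plan does not require the reader to be unaware of flow, and the identity coding does not fill that gap. Any flow-dependent miscount would be systematic and would pass directly into the flow comparison; that conclusion needs no numerical assumption.

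The documents do not establish that such miscounting will occur, or its direction or size. The percentages above show only that an error of about one swallow per 10-minute window could matter with 50 participants. They should not be quoted as properties of this trial.

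The change is worth making because it is cheap, and because counts made with flow known can be repaired only by reading the traces again.

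**What to change.** Add to the Swallowing Frequency section:

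- Each 10-minute recording is saved under a random code that hides participant, flow, period and age group.
- Whoever does the counting scores the files offline, in random order across participants, using one swallow-identification rule written beforehand and applied identically to all conditions.
- Codes are linked to flow only after all counts are locked.

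The identification rule should not be a fixed minimum amplitude or duration. Amplitude and timing are themselves outcomes that flow may change, so a cutoff could drop more swallows at some flows than at others. Masking would not remove that error.

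Apply the same coding to the bolus waveforms if onset, offset or peak are marked by hand, and state in the Swallowing Effort section whether they are.

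The cost is a short protocol addition and some file handling, with counts not available on the day. No extra reader or procedure is needed. The signals are already recorded on the workstation. That it allows recordings to be separated and relabelled is an assumption to confirm, since the protocol does not describe export.
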